7.1. Study Patients

7.1.1. Disposition of Patients

A summary of patient disposition for all patients will be presented and will include a summary of the number and percentage of screened patients, screen failures, and treated patients. The number and percentage of patients who completed the study through the end of the Primary Evaluation period or discontinued/withdrew from the study through the end of the Primary Evaluation period, along with reason for discontinuation/withdrawal will be presented.

The number and percentage of patients in each analysis set will be tabulated.

By-patient data listings with disposition will be provided as well as a listing of patients who did not meet the inclusion/met the exclusion criteria.

7.1.2. Protocol Deviations

Important protocol deviations will be determined per the standard operating procedure (SOP) "Identification, Handling, and Documentation of Protocol Deviations" (SOP-G-CL-0044). The number and percent of patients with specific protocol deviations will be summarized for all enrolled patients by major deviations.

A by-patient listing of inclusion/exclusion criteria, as well as protocol deviations will be presented, separately.

7.1.3. Demographics, Disease Characteristics, and History

All demographic and baseline characteristics information will be summarized using the FAS Set. Summary statistics will be presented by naïve, previously eculizumab-treated patients and total.

By-patient listings of demographic information, disease characteristics, PNH medical history, and medical/surgical history will be produced.

7.1.3.1. Demographics

The following demographic variables will be summarized:

- Sex
- Race
- Ethnicity
- Age (years) at first study drug infusion: descriptive statistics (n, mean, median, SD, minimum, maximum) and frequency of patients in the following categories: ≤ 12 , > 12 years
- Baseline Weight: descriptive statistics (n, mean, median, SD, minimum, maximum) and frequency of patients in the following categories in kg: ≥ 5 to < 10 , ≥ 10 to < 20 , ≥ 20 to < 30 , ≥ 30 to < 40 , ≥ 40 to < 60 , ≥ 60 to < 100 and ≥ 100 .
- Baseline Height
- Baseline Body Mass Index (BMI)
- Patients of Japanese Descent

7.1.3.2. Characteristics and PNH Medical History

The following PNH disease characteristics will be summarized.

- Age (years) at PNH diagnosis.
- Age (years) at first eculizumab infusion.
- Method of PNH diagnosis.
- Years from PNH diagnosis to informed consent.
- PNH clone size at screening.
- Packed red blood cell (pRBC) transfusion requirements in the year prior to receiving ALXN1210 including number of transfusion episodes and units transfused.
- All PNH symptoms experienced at any time prior to informed consent.
- All PNH-associated conditions that were diagnosed at any time prior to informed consent.
- History of any major adverse vascular event (MAVE). The number of patients (n, %) with any history of MAVE and within a particular MAVE category (e. thrombophlebitis/deep vein thrombosis, pulmonary embolus, myocardial infraction, etc.) will be displayed.

7.1.3.3. Medical / Surgical History and Baseline Physical Examination

Medical history will be classified by System Organ Class (SOC) and Preferred Term (PT) using the latest available version of standardized (MedDRA) and will be summarized by naïve, previously eculizumab-treated patients and total for the Safety Set. Likewise, baseline physical examination information will be summarized by naïve, previously eculizumab-treated patients and total for the Safety Set.

7.1.4. Prior and Concomitant Medications / Therapies

Prior and concomitant medications will be summarized using the Safety set. Prior medications are defined as medications taken prior to the first study infusion and include all medications taken within 28 days prior to informed consent as well as all *Neisseria meningitidis* vaccinations administered within 3 years of dosing with ALXN1210, and vaccination history for *Haemophilus influenzae* type b (Hib) and *Streptococcus pneumoniae* from birth. Concomitant medications are defined as medications received by the patients on/after first study infusion.

Medications will be coded using the World Health Organization Drug Dictionary version in use by Alexion at the time of the analysis. Medication summaries i.e. number (%) of patients using prior and concomitant medications will be presented by WHO-DRUG Anatomical Therapeutic Chemical (ATC) and by WHO-DRUG generic name.

Listings of prior and concomitant medications will be produced. A by-patient listing of meningococcal, Hib and *S pneumoniae* from birth vaccinations will be produced showing the date of vaccinations for each patient.

7.2. Efficacy Analyses

All pharmacokinetic analyses will be conducted on the PK Analysis Set. Pharmacodynamic analyses will be conducted on the PD Analysis Set. Analysis of secondary efficacy will be performed on the Full Analysis Set (FAS).

7.2.1. Primary Analysis

This study is descriptive in nature and not statistically powered for hypothesis testing due to the rarity of disease in pediatric patients. Analyses will be conducted separately for naïve and previously eculizumab-treated patients.

Sparse PK and PD (free C5) samples will be collected over the course of the study. Individual serum concentration data will be used to derive PK parameters for ALXN1210. Graphs of mean serum concentration-time profiles will be constructed. Graphs of serum concentration-time profiles for individual patients may also be generated. Actual dose administration and sampling times will be used for all calculations. Descriptive statistics (mean, SD, CV, median, minimum, maximum, geometric mean, and geometric %CV) will be calculated for serum concentration data at each sampling time, as appropriate.

Descriptive statistics will be presented for all ALXN1210 PD endpoints at each sampling time. The PD effects of ALXN1210 administered IV will be evaluated by assessing the absolute values and changes and percentage changes from baseline in total and free C5 serum concentrations and change from baseline in cRBC hemolysis over time, as appropriate.

7.2.1.1. Handling of Dropouts or Missing Data

Missing data for secondary endpoints analyses will be handled as indicated for the specific analysis.

Missing data for QOL instruments will be handled as specified in the instructions for each instrument and as specified in Section 9.4.

7.2.1.2. Subgroup Analysis

Summaries will be presented as indicated for the specific analysis by naïve, previously eculizumab-treated patients and total. No other subgroup analyses are planned due to the small sample size.

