14.10. Pharmacokinetic/Pharmacodynamic Analyses

Individual serum concentration data for all patients who receive at least 1 dose of ALXN1210 and who have evaluable PK data will be used to derive PK parameters for ALXN1210.

Graphs of mean serum concentration-time profiles will be constructed. Graphs of serum concentration-time profiles for individual patients may also be provided. Actual dose administration and sampling times will be used for all calculations. Descriptive statistics will be calculated for serum concentration data at each sampling time, as appropriate. Assessment of population-PK may be considered using data from this study or in combination with data from other studies.

Pharmacodynamic analyses will be performed for all patients who receive at least 1 dose of ALXN1210 and who have evaluable PD data.

Descriptive statistics will be presented for all ALXN1210 PD endpoints at each sampling time (Section 7.3). The PD effects of ALXN1210 administered IV will be evaluated by assessing the absolute values and changes and percentage changes from baseline in total and free C5 serum concentrations and change from baseline in cRBC hemolysis over time, as appropriate. Assessments of ALXN1210 PK/PD relationships may be explored using data from this study or in combination with data from other studies. Analyses will be conducted separately for naïve and previously eculizumab-treated patients.

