4. DESCRIPTION OF THE PROTOCOL

ALXN1210-PNH-304 is a Phase 3, open-label, single-arm multicenter study to evaluate the PK/PD, safety, and efficacy of ALXN1210 administered by intravenous (IV) infusion to pediatric patients (< 18 years of age) with paroxysmal nocturnal hemoglobinuria (PNH). The study consists of a 4-week Screening Period, a 26-week Primary Evaluation Period, and an Extension Period.

Patients will receive a loading dose of ALXN1210 on Day 1, followed by maintenance dosing of ALXN1210 on Day 15 and q8w thereafter for patients weighing ≥ 20 kg, or q4w for patients weighing < 20 kg, as shown in Table 2. With the agreement of the Alexion Medical Monitor, the 600 mg loading dose may be given to patients weighing ≥ 5 to < 10 kg as 2 separate infusions administered no more than 24 hours apart. Dosages are based on the patient's body weight recorded on the day of dosing or the most recently recorded weight. For patients entering the study on eculizumab therapy, Day 1 of study treatment will occur 2 weeks from the patient's last dose of eculizumab.

Table 2: Loading and Maintenance Treatment Regimens

Body Weight Range (kg) ^a	Loading Dose (mg)	Maintenance Doses (mg)	Maintenance Dosing Frequency
≥ 5 to < 10	600 ^b	300	q4w
≥ 10 to < 20	600	600	q4w
≥ 20 to < 30	900	2100	q8w
≥ 30 to < 40	1200	2700	q8w
≥ 40 to < 60	2400	3000	q8w
≥ 60 to < 100	2700	3300	q8w
≥ 100	3000	3600	q8w

^a Dose regimen will be based on body weight obtained at the study visit. If the study drug needs to be prepared the night prior to the visit, the weight from the previous visit may be used.

^b With the agreement of the Alexion Medical Monitor, the 600 mg loading may be given to patients weighing ≥ 5 to < 10 kg as 2 separate infusions administered no more than 24 hours apart.

Abbreviations: q4w = once every 4 weeks; q8w = once every 8 weeks

With the agreement of the Alexion Medical Monitor, administration of a supplemental dose of ALXN1210 is permitted.

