An interim analysis of data, including ALXN1210 PK and free C5 levels, will be conducted after 4 patients weighing ≥ 5 kg to < 40 kg have completed dosing through Day 71. Enrollment of patients will proceed without interruption while the analysis is ongoing. The accrued safety and PK/PD data will be assessed to ensure that ALXN1210 treatment is well tolerated and is providing adequate complement inhibition. Based on this review, the dose regimen may be adjusted. In addition, an independent Data Monitoring Committee (DMC) will review safety data from the study on a regular basis. Prior to the initiation of the study, the committee will develop a charter to describe their activities and responsibilities.

To support regulatory filings, interim analyses may be conducted based on efficacy, safety, PK, PD, and immunogenicity data collected through the end of the 26-week Primary Evaluation Period (Day 183) after 12 patients are enrolled, and after enrollment is completed.

After completion of all pre-dose assessments on Day 183, all patients will enter an Extension Period and continue to receive ALXN1210 according to the appropriate weight-based regimen. The Extension Period will continue until the product is registered or approved (in accordance with country-specific regulations) or for up to 4 years, whichever occurs first, except in Norway where the Extension Period will be 4 years. The end of study is defined as the last patient's last visit or follow-up (whether on site or via phone call) in the Extension Period.

The study objectives are as follows:

The objectives of this study are to assess the pharmacokinetics (PK), pharmacodynamics (PD), safety, and efficacy of ALXN1210 in pediatric patients with paroxysmal nocturnal hemoglobinuria (PNH). Additional information about the study can be found in the protocol.

To support regulatory filings, interim CSRs may be prepared based on efficacy, safety, PK, PD, and immunogenicity data collected through the end of the 26-week Primary Evaluation Period (Day 183) after 12 patients are enrolled, and after enrollment is completed. This statistical analysis plan (SAP) outlines only the analyses that are to be included in the report developed after the 26-week Primary Evaluation Period after 12 patients are enrolled. A final CSR to summarize long-term efficacy, safety, PK, PD, and immunogenicity parameters will be produced at study completion.

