5. DEFINITIONS

5.1. Efficacy

5.1.1. Primary Endpoint(s)

Pharmacokinetic/Pharmacodynamic parameters (trough and peak) at baseline and Weeks 2, 10, 18, and 26

- PK: maximum serum concentration (C_{max}), trough serum concentration (measured at end of dosing interval at steady state; C_{trough}), accumulation ratio
- PD: change in free C5 concentrations and in chicken red blood cell (cRBC) hemolytic activity over time.

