7. STATISTICAL ANALYSIS

All data collected in this study will be documented using summary tables, figures, and data listings. For categorical variables, frequencies and percentages will be presented by naïve, previously eculizumab-treated patients and total; for continuous variables, descriptive statistics (n, mean, median, standard deviation [SD], minimum, maximum) will be presented by naïve, previously eculizumab-treated patients and total.

Descriptive statistics for PK parameters will include the number of observations, mean, SD, coefficient of variance (CV), median, minimum, maximum, geometric mean, and geometric %CV.

Clinical central laboratory samples that meet the definition of TTH will be identified and all potassium, ALT, AST, magnesium, phosphorous, and LDH samples affected by TTH will be excluded from analysis of all efficacy and safety endpoints, with the exception that the LDH values will be used for the qualification of breakthrough hemolysis. The TTH samples from the central lab will be defined as having serum potassium ≥ 6 mmol/L and LDH $\geq 2 \times$ ULN.

A small portion of the data may not go through source data verification (SDV) process due to the COVID-19 pandemic. The non-SDV'd data will be flagged in listings.

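### The primary PK/PD summaries and mean profiles are not separated by dosing interval or weight band, which limits how they can be read, most of all if any patient under 20 kg enrols

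*SAP*

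**What the plan says.** SAP section 7 sets the general layout: "descriptive statistics (n, mean, median, standard deviation [SD], minimum, maximum) will be presented by naïve, previously eculizumab-treated patients and total". SAP 7.2.1 calls for separate analysis of naïve and previously treated patients, as does Protocol 14.10: "Analyses will be conducted separately for naïve and previously eculizumab-treated patients". SAP 7.2.1.2 closes the list: "No other subgroup analyses are planned due to the small sample size".

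On graphs, SAP 7.2.1 makes the mean profile firm and the individual profile optional: "Graphs of mean serum concentration-time profiles will be constructed. Graphs of serum concentration-time profiles for individual patients may also be generated". Population PK is also optional (SAP 7.2.3).

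The regimen differs by weight. SAP section 4 gives "q8w thereafter for patients weighing ≥ 20 kg, or q4w for patients weighing < 20 kg", and SAP Table 2 sets loading and maintenance doses for seven weight bands. Outside that table, the seven bands appear in the SAP only as a baseline frequency count (7.1.3.1).

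SAP 5.1.1 lists the primary PK parameters as Cmax, Ctrough, defined as "trough serum concentration (measured at end of dosing interval at steady state", and an accumulation ratio. It gives no numerator, reference dose or interval for that ratio.

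**The concern.** PK/PD is the primary endpoint, and two features that shape concentrations change with weight: the maintenance interval and the step from loading to maintenance dose. Neither defines a column or a curve in the committed displays. A mean Ctrough can therefore combine values taken 28 and 56 days after a dose. A mean curve can join patients redosed between sampling visits to patients who were not. A mean accumulation ratio can combine patients whose dose halved after loading with patients whose dose more than doubled.

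Protocol 9.4 says weight-based dosing is meant to limit exposure differences between weights. A reader would look to the primary PK displays for that, and they are not arranged to show it.

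**Working it through.** The plan gives no half-life and no accumulation figure, so there is nothing of its own to reproduce. The first two steps use only the documents. The rest rests on an assumed model.

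**1. Dosing history at the shared sampling days** (Protocol Table 1). Maintenance falls on Days 15, 43, 71, 99, 127 and 155 for q4w, and on Days 15, 71 and 127 for q8w. Maintenance doses already given:

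| Predose sample | q4w | q8w |
|---|---|---|
| Day 71 | 2 | 1 |
| Day 127 | 4 | 2 |
| Day 183 | 6 | 3 |

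The trough on each of these days closes 28 days for q4w and 56 for q8w. No PK sample is scheduled on Days 43, 99 or 155, so a line from the Day 15 end-of-infusion value to the Day 71 predose value spans one decline for q8w and a redosing for q4w.

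**2. Maintenance/loading dose ratio** (SAP Table 2), lightest band to heaviest: 300/600 = 0.50; 600/600 = 1.00; 2100/900 = 2.33; 2700/1200 = 2.25; 3000/2400 = 1.25; 3300/2700 = 1.22; 3600/3000 = 1.20. Within q8w alone the range is 1.20 to 2.33.

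**3. Effect on the accumulation ratio.** Assumptions: one compartment, linear kinetics, instantaneous input, no supplemental dose, and the same half-life h at every weight, from 20 to 60 days.

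- Theoretical steady-state ratio: R = 1/(1 − 2^(−τ/h)), with τ = 28 or 56 days. The q4w/q8w quotient is 1 + 2^(−28/h).
- Observed peak ratio: sum the remaining fraction 2^(−days/h) of every dose through Day 183, then divide by the peak on the reference day. Volume cancels within a patient.

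Example, 20 to < 30 kg, h = 40:
- Day 183 peak = 2100 × (1 + 0.379 + 0.144 + 0.054) + 900 × 0.043 ≈ 3350.
- Against Day 1: 3350/900 = 3.72.
- Against Day 15: 3350/(2100 + 900 × 0.785) = 3350/2806 = 1.19.

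q4w against q8w (observed means weight the bands equally):

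| h (days) | R, q4w | R, q8w | Quotient | Day 183/Day 1 peak, q4w mean | q8w mean | Quotient |
|---|---|---|---|---|---|---|
| 20 | 1.61 | 1.17 | 1.38 | 1.21 | 1.93 | 0.63 |
| 30 | 2.10 | 1.38 | 1.52 | 1.57 | 2.28 | 0.69 |
| 40 | 2.60 | 1.61 | 1.62 | 1.93 | 2.65 | 0.73 |
| 50 | 3.11 | 1.85 | 1.68 | 2.26 | 3.00 | 0.75 |
| 60 | 3.62 | 2.10 | 1.72 | 2.55 | 3.33 | 0.77 |

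Spread across weight bands within q8w:

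| h (days) | Day 183/Day 1 range | Fold | Day 183/Day 15 fold |
|---|---|---|---|
| 20 | 1.40 to 2.73 | 1.94 | 1.20 |
| 30 | 1.66 to 3.21 | 1.94 | 1.22 |
| 40 | 1.93 to 3.72 | 1.92 | 1.22 |
| 50 | 2.20 to 4.21 | 1.91 | 1.22 |
| 60 | 2.45 to 4.65 | 1.90 | 1.22 |

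The two definitions put q4w on opposite sides of q8w. Changing the reference from the loading dose to the first maintenance dose removes most of the spread within q8w. No figure is offered for free C5 or cRBC hemolysis, because the documents give no exposure-response model.

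**The case against.** The strongest reply is that little is lost.

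- Each patient's own peak and trough are valid for that patient's interval, and the SAP commits to real times: "Actual dose administration and sampling times will be used for all calculations". This stands.
- A reader might infer that the planned tables cannot show whether inhibition lasts through the dosing interval. The documents do not support that. Scheduled predose samples on Days 71, 127 and 183 fall at the end of each patient's own interval under either regimen, and free C5 is summarized at each sampling time with minimum and maximum. A loss of inhibition in any patient would show in the maximum.
- Overall exposure variability is reported through CV and geometric %CV, although not the part due to weight.
- Protocol 14.1 commits to detailed listings of all data and derived outcomes. With about 13 patients, every value can be inspected.
- The interim PK and free C5 review "will be conducted after 4 patients weighing ≥ 5 kg to < 40 kg have completed dosing through Day 71", so the lighter bands get specific attention. That group can itself contain both intervals.
- A total column for PK/PD is not certain. SAP section 7 lists it generally, but 7.2.1 and Protocol 14.10 mention only the two treatment-history groups. Pooling within each of those groups remains.
- Small numbers are a fair reason against full tables: 13 patients over 7 bands and 2 history groups is 13/14, or about 0.9 per cell. They are not a reason against marking individual values.

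A reader might also take 1.38 to 1.72, or a percentage shift in a pooled mean built on it, as the bias. That quotient comes from a formula for equal repeated doses, which the documents do not say will be used, and loading and maintenance doses differ in six of the seven bands. The roughly 1.9-fold spread within q8w likewise belongs to a Day 1 reference only.

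**Conclusion.** The point holds as a limit on how the primary displays can be read. The committed summaries and mean profiles do not separate dosing interval or weight band, and the tools that could do so are optional. If any patient under 20 kg enrols, that patient's treatment-history stratum mixes 28-day with 56-day troughs and redosed with single-interval curves. If none does, the interval problem disappears and only the dose-ratio spread within q8w remains: about 1.9-fold on a Day 1 reference and about 1.2-fold on a Day 15 reference, under the assumed model.

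No single bias figure is defensible. The direction for the accumulation ratio depends on its unstated definition, and the size depends on the half-life and on how many q4w patients enrol, neither of which the documents give. The data are not invalidated, and nothing in the sample size or inference changes, since the study is descriptive.

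**What to change.** Amend SAP 7.2.1 and 7.2.1.2, with the ratio definition carried into 5.1.1:

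1. Make individual concentration-time and free C5 profiles mandatory, marked by dosing interval and weight band.
2. Do not average concentration profiles, troughs or accumulation ratios across q4w and q8w. Where q4w patients are few, show them as individual values.
3. Define the accumulation ratio within patient: numerator, reference dose and interval. If the reference is the loading dose, label it an observed ratio.

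This is a cheap improvement: SAP wording, plot symbols and table layout, with no new samples or visits. The downside is small cells, which is the SAP's own reason for planning no further subgroups. Showing individual values, and not crossing interval with treatment history, answers it. If no patient under 20 kg enrols, the q4w display is empty and the weight-band marking still helps.

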7.2.1.3. Multicenter Studies

This is a multicenter study; however, the expected sample size is not sufficient to perform any meaningful efficacy summaries by center.

7.2.1.4. Hypothesis Testing and Significance Level

This study is descriptive in nature and not statistically powered for hypothesis testing. Estimates of treatment effect on some of the efficacy parameters will be accompanied by two-sided 95% confidence intervals, as indicated for the specific analysis.

7.2.1.5. Sensitivity Analyses

Presented in Section 7.2.2 last observation carried forward (LOCF) will be the sensitivity analyses for the secondary efficacy endpoints if applicable.

7.2.2. Secondary Analyses

Descriptive statistics for the secondary endpoints will be produced for each visit where applicable, by naïve, previously eculizumab-treated patients and total.

- Percentage change in LDH from baseline to Day 183 (Week 26)
 - Absolute LDH levels, and the change and percent change from baseline, will be summarized at all study visits up to Day 183 (Week 26) by both observed case (OC) and LOCF. Baseline is defined as the average of all assessments analyzed by the central laboratory prior to first study drug administration.
 - The number (%) of patients achieving LDH levels at or below 1.0 times upper limit of normal ($1.0 \times \text{ULN}$) and levels at or below $1.5 \times \text{ULN}$ will be displayed.
 - Mean ($\pm 95\%$ CI) of absolute LDH levels, and the change and percent change from baseline will be plotted over time, by naïve and previously eculizumab-treated patients.
- Transfusion avoidance (TA)
 - Point estimates and 2-sided 95% exact CIs will be computed. Patients who withdraw from the study due to lack of efficacy during the Primary Evaluation Period will be considered as non-responders and will be counted in the group

- needing transfusion. For patients who withdraw from the study for any other reason during the Primary Evaluation Period, their data up to the time of withdrawal will be used to assess TA.
- A summary of the number of pRBC transfusion requirements up to Day 183 study will be presented including number of transfusion episodes and units transfused.
 - Change in quality of life (QoL), as measured by Pediatric FACIT-Fatigue questionnaire from baseline to Day 183 (Week 26)
 - The scoring guideline for the Pediatric FACIT-Fatigue instrument will be used to calculate a FACIT-Fatigue score. Please refer to Section 9.4 for a more detailed description of the Pediatric FACIT-Fatigue score and the scoring methods.
 - Absolute scores, change from baseline, and percent change from baseline in FACIT-Fatigue scores will be summarized by both OC and LOCF at baseline and at the study visits where this assessment is collected up to Day 183 (Week 26).
 - At each study visit, the proportion of patients who showed an improvement of at least 3 points for the Pediatric FACIT-Fatigue scores will be summarized by point estimates and 2-sided 95% exact CIs.
 - Proportion of patients with stabilized hemoglobin
 - Point estimates and 2-sided 95% exact CIs will be computed. Patients who withdraw from the study due to lack of efficacy during the Primary Evaluation Period will be considered as non-responders and will be counted in the group who did not meet the stabilized hemoglobin definition. For patients who withdraw from the study for any other reason during the Primary Evaluation Period, their data up to the time of withdrawal will be used to assess stabilized hemoglobin.
 - Percentage change in free hemoglobin from baseline to Day 183 (Week 26)
 - Absolute free hemoglobin values, and the change and percent change from Baseline, will be summarized by both OC and LOCF at all study visits up to Day 183 (Week 26). Baseline is defined as the last non-missing assessment value prior to the first study drug infusion.
 - Mean (\pm 95% CI) of free hemoglobin, and the change and percent change from baseline will be plotted over time, by naïve and previously eculizumab-treated patients.
 - Proportion of patients with breakthrough hemolysis
 - Point estimates and 2-sided 95% exact CIs will be computed. Patients who withdraw from the study due to lack of efficacy during the Primary Evaluation Period will be considered as non-responders and will be counted in the group with breakthrough hemolysis. For patients who withdraw from the study for any other reason during the Primary Evaluation Period, their data up to the time of withdrawal will be used to assess breakthrough hemolysis.
 - The number of any treatment emergent MAVEs (n) and number of patients with events (n, %) will be displayed. Each of the MAVE categories will be similarly

summarized. Patients having multiple MAVEs within a category will be counted once in that category.

By-patient data listings containing all secondary endpoints will be produced.

